12.5. Other Observational Points

Summary statistics at each timepoint, as well as changes from baseline over time, will be presented for the MSIS-29 physical and psychological scores for measuring patient impression of impact of MS. Summary statistics over time will be presented for the Physician's CGI-I score for walking ability.

12.6. Interim Analyses

No formal interim analyses are planned. Safety data will be analyzed at least annually once enrollment has begun. Summary reports will be submitted annually with Fampyra Periodic Safety Update Reports (PSURs). Early identification of any potential safety signals to elderly patients will be evaluated by reviewing adverse drug reactions for patients aged 65 years or older. These data will be reviewed as they are received on the safety database and will be further assessed in the periodic (i.e., monthly) signal review and as part of the PSUR.

12.7. Sample Size Considerations

12.7.1. Patient Sample Requirement

This study is exploratory in nature, and no confirmatory statistical testing will be performed.

Seizures

In a cohort study of MS patients with a known background incidence rate of seizures of 0.003 per patient-year [Eriksson 2002], a sample of 3308 patients has 80% power to detect a doubling of the seizure rate when the significance level is 0.05.

Cardiac Conduction Disorders

Information on cardiac conduction disorders in the MS population is limited, but the prevalence rate of arrhythmias and conduction disorders in MS patients aged 65 years and older was reported in a study to be 1% [Fleming and Blake 1994]. If this rate is used as background incidence, a sample of 3308 patients has 99% power to detect an incidence of 2% of arrhythmias and conduction disorders over 1 year of follow-up.

The most recent publication on cardiovascular outcomes in MS patients was used to determine the background rate of atrial fibrillation [Christiansen 2010] (0.1% for atrial fibrillation/flutter). A sample size of 3308 patients has 46% power to detect a 2-fold increase in atrial fibrillation over 1 year of follow-up.

CONFIDENTIAL

The information contained herein may not be used, disclosed, or published without the written consent of Biogen Idec MA Inc.

Background rates are not readily available for the other events based on the safety profile in the clinical development program; thus, power calculations are not feasible.

Based on the assumption that approximately 34% of patients will drop out or discontinue treatment, at least 5000 MS patients will be enrolled to ensure 3308 evaluable patients treated for 1 year. The maximum number of patients to be enrolled can be adjusted on an ongoing basis to reflect the dropout rate.

CONFIDENTIAL

The information contained herein may not be used, disclosed, or published without the written consent of Biogen Idec MA Inc.

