The information contained herein may not be used, disclosed, or published without the written consent of Biogen Idec MA Inc.

from baseline over time, will be presented for the MSIS-29 score for the physical and psychological impact of MS. Summary statistics over time will be presented for the Physician's CGI-I score for walking ability.

Interim Analysis: No formal interim analyses are planned. Safety data will be analyzed at least annually once enrollment has begun. Summary reports will be submitted annually with Fampyra Periodic Safety Update Reports.

Sample Size Determination: Approximately 5000 MS patients will be enrolled in the study and followed for approximately 1 year after the start of Fampyra treatment to collect at least 3308 patient-years of exposure to Fampyra based on a dropout rate of 34%.

The sample size is calculated based on seizure rates in MS patients. A sample of 3308 patients would achieve 80% power to detect a doubling of seizure rates, assuming a background incidence rate of 0.003 per patient-year [Eriksson 2002] when the significance level is 0.05.

Given this sample of 3308 patients and published background incidence on cardiovascular outcomes in MS patients (1% for arrhythmias and conduction disorders in patients aged 65 years or older [Fleming and Blake 1994], 0.1% for atrial fibrillation/flutter [Christiansen 2010]), the power to detect a doubling of events in 1 year of follow-up is 99% for any arrhythmias and conduction disorders and 46% for atrial fibrillation.

Study Stopping Rules: Biogen Idec may terminate this study, after informing the Investigators, at any time. The Investigators will be notified by Biogen Idec if the study is placed on hold, completed, or closed.

CONFIDENTIAL

The information contained herein may not be used, disclosed, or published without the written consent of Biogen Idec MA Inc.

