5.2. Study Rationale

Due to the inherent constraints of clinical trials, the existing Fampyra safety database established during the development phase has its limitations, for example, the number of patients aged ≥ 65 years was limited and patients with pre-existing cardiovascular risk factors were excluded from the studies. Therefore, understanding of safety issues in these patient subpopulations is limited. It is expected that these patients will be represented in this observational study to be conducted in postmarketing routine practice setting and will help understand the safety profiles in these subpopulations not yet fully studied during the development phase.

Specifically, premarketing clinical trials were not powered to evaluate the incidence of rare AEs, including seizure. This observational study is powered to detect a doubling in the incidence of seizures in the MS patient population to further assess if Fampyra treatment is associated with an increased seizure rate.

Furthermore, a 3.6% higher incidence of urinary tract symptoms (8.4% in placebo-treated patients versus 12.0% in Fampyra-treated patients) was observed based on data from 3 pooled premarketing placebo-controlled clinical trials; however, it is not fully understood if the event was a result of infection or sensory overstimulation. This study is also aimed to improve quantification of urinary tract symptoms as either culture-confirmed infection or culture-negative symptomatology.

CONFIDENTIAL

The information contained herein may not be used, disclosed, or published without the written consent of Biogen Idec MA Inc.

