9. TREATMENT OF PATIENTS

9.1. Fampyra Treatment

Fampyra is commercially available and is a prolonged-release tablet containing 10 mg active substance 4-AP and excipients.

Fampyra will not be supplied for this study. The Investigators will follow standard local procedures for prescribing commercial Fampyra. No reference therapies will be included in the study.

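### The 99% power for arrhythmias and conduction disorders is not supported for this cohort: it uses a prevalence from MS patients aged 65 and older as a 1-year incidence for all 3308 patients

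*Protocol*

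**What the plan says.** Protocol Section 12.7.1, under Cardiac Conduction Disorders, first notes that information in MS is limited. It then says that the "prevalence rate of arrhythmias and conduction disorders in MS patients aged 65 years and older was reported in a study to be 1"%. The next sentence turns this into a planning rate: "If this rate is used as background incidence, a sample of 3308 patients has 99% power to detect an incidence of 2"% over 1 year of follow-up.

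The synopsis (Sample Size Determination) describes the same input as "published background incidence on cardiovascular outcomes in MS patients (1% for arrhythmias and conduction disorders in patients aged 65 years or older"). It then says that "the power to detect a doubling of events in 1 year of follow-up is 99% for any arrhythmias and conduction disorders". The age limit is still shown there. The word prevalence and the conditional clause are not.

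Other parts of the protocol bear on the point:

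- The eligibility criteria (Section 8.2) set no age limit.
- Section 12.4 summarises events separately for patients aged 65 and older and for those under 65, so both groups are expected.
- There is no comparator (Section 9.1): "No reference therapies will be included in the study". The calculation therefore sets one cohort against a fixed external rate.
- Among the reasons for the study, Section 5.2 gives that in the premarketing trials "the number of patients aged ≥ 65 years was limited and patients with pre-existing cardiovascular risk factors were excluded from the studies".

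**The concern.** Two things do not match.

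**Population.** The 1% describes MS patients aged 65 and older. The 3308 patients are of any age, and the protocol does not say how many will be 65 or older. Only that subgroup can be set directly against a figure for that age group. For the whole cohort an all-age rate is needed, and none is given.

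**Measure.** A prevalence counts people who already have the condition. The study counts events during 1 year of follow-up. Section 10.1 records conduction disorder as a baseline risk factor, so some patients are expected to enter with it, and a condition already present is not a new event.

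Cardiac disorders are among the AEs of particular interest (Section 11.2.2), and limited data in patients aged 65 and older is a stated reason for the study. A reader who takes 99% as the study's sensitivity could read more reassurance into an unremarkable arrhythmia rate than the plan can support.

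**Working it through.** **Inputs from the protocol.** Background p0 = 1% and alternative p1 = 2% (Section 12.7.1); n = 3308 evaluable patients followed for 1 year (Section 12.7.1); significance level 0.05 (stated in the seizure paragraph, sidedness not given); no comparator (Section 9.1).

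**Method.** A one-sample test of a proportion against a fixed rate, normal approximation, two-sided 0.05:

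Power = Φ[(p1 − p0 − 1.96·√(p0(1−p0)/n)) / √(p1(1−p1)/n)]

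**Step 1: reproduce the protocol's figures (n = 3308).**

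For arrhythmias, √(0.01·0.99/3308) = 0.001730 and √(0.02·0.98/3308) = 0.002434. So (0.01 − 1.96·0.001730)/0.002434 = 2.715, and Φ(2.715) = 99.7%.

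| Event | p0 | p1 | Computed | Stated |
|---|---|---|---|---|
| Arrhythmias and conduction disorders | 1% | 2% | 99.7% | 99% |
| Seizures | 0.3% | 0.6% | 80.1% | 80% |
| Atrial fibrillation/flutter | 0.1% | 0.2% | 46.0% | 46% |

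One method matches all three stated powers, so it is very probably the one used. It also shows that the 99% takes all 3308 patients at the 1% rate.

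**Step 2: keep 1% against 2%, but count only patients aged 65 and older.** The share is not in the protocol; the values below are assumptions. The shortfall of prevalence as a measure of incidence is left uncorrected here.

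| Assumed share aged ≥65 | n | Power |
|---|---|---|
| 5% | 165 | 32% |
| 10% | 331 | 46% |
| 20% | 662 | 67% |
| 30% | 992 | 80% |
| 50% | 1654 | 93% |

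For example, with n = 331: (0.01 − 1.96·0.005469)/0.007695 = −0.093, and Φ(−0.093) = 46%. By the same formula 80% power needs n = 979, and 99% needs n = 2712, which is 2712/3308 = 82% of the sample.

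**Step 3: keep all 3308 patients, but vary the all-age 1-year incidence and double it.** The incidence is again an assumption.

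| Assumed all-age incidence | Doubled to | Power |
|---|---|---|
| 0.1% | 0.2% | 46% |
| 0.2% | 0.4% | 67% |
| 0.3% | 0.6% | 80% |
| 0.5% | 1.0% | 93% |
| 0.8% | 1.6% | 99% |

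**Step 4: sensitivity to the test.** An exact binomial test with upper tail at most 0.025 gives lower power for the Step 2 subgroups: 12%, 34%, 56% and 77% at n = 165, 331, 662 and 992. Part of the drop comes from discreteness: at n = 165 the attained tail is only 0.007. The normal approximation is kept as the main result because it matches the protocol's own figures.

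**The case against.** The best defence is disclosure. Section 12.7.1 says that information is limited, calls the 1% a prevalence, gives the age limit, and makes the power conditional on using that rate as an incidence. The synopsis keeps the age limit. The study is declared exploratory with no confirmatory testing, seizures set the sample size, and the protocol reports a low power where it finds one (46% for atrial fibrillation).

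Much of this stands, and it limits the weight of the point. It does not remove it. The condition in Section 12.7.1 covers the step from prevalence to incidence; nothing covers the step from patients aged 65 and older to all ages. In the synopsis the condition is gone and the same number is called an incidence, so the two sections disagree about what the 1% is.

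Three stronger readings are tempting, and the protocol does not support them:

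- *The calculation is wrong.* It is not: 99.7% follows from the stated inputs. The problem is the choice of input.
- *The study cannot have 99% power.* This is not shown. With an all-age incidence of about 0.8% or more, a doubling would still be detected with about 99% power.
- *Power among patients aged 65 and older is half or less.* This holds by the protocol's method only up to a share of roughly 10%; at 30% it is 80%. The protocol gives no share.

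Nor is the analysis by age missing. Section 12.4 already plans summaries by age group and person-year rates for AEs of particular interest. How new-onset events are defined may properly be left to the statistical analysis plan.

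**Conclusion.** The point holds as a matter of input and wording. The 99% is not supported for this cohort because it rests on a prevalence in patients aged 65 and older, used as an all-age 1-year incidence. The synopsis makes this worse by calling the figure an incidence without condition.

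How far the true power lies from 99% cannot be settled from the protocol. It is about 32% to 80% in the older subgroup for assumed shares of 5% to 30%, and about 46% to 99% for all ages at assumed incidences of 0.1% to 0.8%. All these figures assume the one-sample, two-sided normal method that reproduces the protocol's three stated powers.

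Severity is moderate: a stated power needs correcting on a question that the study was partly set up to address, but no sample size and no confirmatory test depends on it.

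**What to change.** In Section 12.7.1 and in the synopsis:

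1. Label the 1% in both places as a prevalence reported in MS patients aged 65 and older, and stop calling it background incidence in the synopsis.
2. Remove the unqualified 99%.
3. Replace it with power, or expected 95% confidence interval width, over a stated range of numbers aged 65 and older and a stated range of all-age incidence. The tables above can serve as a start. If an all-age incidence with a source is available, use it as the main case.
4. Make the two sections agree.

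The cost is a few sentences and a less favourable stated power. Patient numbers, data collection and planned analyses do not change.

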13. ETHICAL REQUIREMENTS

Biogen Idec and the Investigators agree to comply with this protocol and to conduct the Fampyra observational study in accordance with Good Pharmacoeconomics Practices, local national laws and regulations applicable to noninterventional studies, and Volume 9A of The Rules Governing Medicinal Products in the European Union (in European Economic Area countries). The patient's privacy, physical and mental integrity, and his/her personality and confidentiality will be strictly respected in accordance with the World Medical Association Declaration of Helsinki.

13.1. Ethics Committee

As regulations for observational studies differ among participating countries, Competent Authorities and Independent Ethics Committees (IECs) will be consulted as dictated by local country regulations.

If an IEC vote is required per local regulations, the Investigator/institution must have written and dated approval/favorable opinion from the IEC for the study protocol/amendment(s), written data consent form, and any data consent form updates before initiating a study. The IEC approval must identify the protocol version as well as the documents reviewed.

13.2. Patient Information and Consent

Prior to any data collection under this protocol, the patient, in accordance with local practice and regulations, must sign a written informed consent. Information about the Fampyra observational study will be explained to the patient. Data will be collected during the year of observation. A copy of the informed consent form, signed and dated by the patient, must be given to the patient. Confirmation of a patient's informed consent must be documented in the patient's medical record prior to any data collection under this protocol. The approved informed consent form must not be altered without the prior agreement of the relevant ethics committee and Biogen Idec.

In order to ensure patient confidentiality, patients will be assigned a unique identifying number. The transmitted data sets use this identifying number plus partial date of birth but are otherwise anonymous.

In any presentations or in publications of the Fampyra observational study results, the patients' identities will remain anonymous and confidential. Biogen Idec, its designee(s), and various government health agencies may inspect the records of the Fampyra observational study. Every effort will be made to keep the patients' personal medical data confidential.

13.3. Registration of Study and Disclosure of Study Results

Biogen Idec will register the study and post study results regardless of outcome on a publicly accessible website in accordance with the applicable laws and regulations.

CONFIDENTIAL

The information contained herein may not be used, disclosed, or published without the written consent of Biogen Idec MA Inc.

14. ADMINISTRATIVE PROCEDURES

14.1. Quality Assurance

During and/or after completion of the study, quality assurance officers named by Biogen Idec or the regulatory authorities may wish to perform onsite audits. The Investigators will be expected to cooperate with any audit and to provide assistance and documentation (including source data) as requested.

14.2. Monitoring of the Study

Biogen Idec or designee representatives may conduct onsite visits to the study facilities for the purpose of monitoring various aspects of the study. The Investigator must agree to Sponsor-authorized personnel having direct access to the patient (or associated) files for the purpose of verifying entries made in the CRF, and assist with their activities, if requested. Adequate time and space for monitoring visits should be made available by the Investigators or study staff.

The site must complete the CRFs in a timely manner and on an ongoing basis to allow regular review by the study team.

14.3. Confidentiality

All information obtained during the conduct of the study with respect to the patient's state of health will be regarded as confidential. The Investigator must ensure that each patient's anonymity is maintained. On CRFs and other documents submitted to Biogen Idec or the Contract Research Organization (CRO), patients must not be identified by name. Instead, patients will only be known by the unique patient number allocated to them in order to ensure confidentiality on all study documentation. Patients will retain this unique number throughout the study. The Investigators will keep a separate log of these codes. For disclosure of any confidential information, an agreement will be obtained in writing.

Documents that are not for submission to Biogen Idec or the CRO (e.g., consent forms) will be maintained by the Investigators in strict confidence, except to the extent necessary to allow monitoring by Biogen Idec and the CRO, and auditing by Competent Authorities. Patient identity will remain confidential in all publications related to the study.

14.4. Study Funding

Biogen Idec is the Sponsor of the study and is funding the study. All financial details are provided in the separate contract(s) between the institution, Investigator, and Biogen Idec.

14.5. Publications

Details are included in the clinical trial agreement for this study.

CONFIDENTIAL

The information contained herein may not be used, disclosed, or published without the written consent of Biogen Idec MA Inc.

15. FURTHER REQUIREMENTS AND GENERAL INFORMATION

Biogen Idec or designee will be responsible for all administrative aspects of this study including, but not limited to, study initiation, monitoring, management of AEs, and data management.

15.1. External Contract Organizations

15.1.1. Contract Research Organization

Quintiles (CRO) will be responsible for administrative aspects of the study including, but not limited to, study initiation, monitoring, management of SAE reports, and data management. Before patients are screened at each study site, the CRO will review study responsibilities with the Investigators and other study site staff, as appropriate.

15.1.2. Electronic Data Capture

Study data will be captured and managed by study sites on electronic CRFs by a web-based electronic data capture tool, which will be formally reviewed and approved by Biogen Idec and Quintiles.

15.2. Changes to Final Study Protocol

All protocol amendments must be submitted to the ethics committee and Regulatory Authorities if required by local law. Protocol modifications that affect patient safety, the scope of the investigation, or the scientific quality of the study must be approved by the ethics committee before implementation of such modifications to the conduct of the study. If required by local law, such modifications must also be approved by the appropriate regulatory agency prior to implementation.

15.3. Study Report Signatory

A final study report will be completed after study end. The final study report will be prepared regardless of whether the study is completed or prematurely terminated. Biogen Idec will provide all Investigators with a summary of the final results. The final study report will be submitted to the regulatory authorities in accordance with applicable regulatory requirements.

CONFIDENTIAL

The information contained herein may not be used, disclosed, or published without the written consent of Biogen Idec MA Inc.

APPENDIX A. PHYSICIAN'S CLINICAL GLOBAL IMPRESSION- IMPROVEMENT (CGI-I) SCALE ON WALKING ABILITY

The Clinical Global Impression-Improvement (CGI-I) scale is a 7-point scale that requires the clinician to rate the improvement or worsening of the overall walking ability of the patient relative to a baseline state at the beginning of Fampyra treatment as follows.

How much has the patient's overall walking ability improved or worsened relative to a baseline status at the beginning of Fampyra treatment?

1 = very much improved

2 = much improved

3 = minimally improved

4 = no change

5 = minimally worse

6 = much worse

7 = very much worse

Adopted and modified based on CGI [[Guy 1976](#)].

CONFIDENTIAL

The information contained herein may not be used, disclosed, or published without the written consent of
Biogen Idec MA Inc.

APPENDIX B. THE MULTIPLE SCLEROSIS IMPACT SCALE (MSIS-29)

MS IMPACT SCALE (MSIS-29) US English translation of the MSIS-29 v1

- The following questions ask for your views about the impact of MS on your day-to-day life **during the past two weeks**
- For each statement, please **circle** the **one** number that **best** describes your situation
- Please answer **all** questions

In the past two weeks , how much has your MS limited your ability to ...	Not at all	A little	Mod-erately	Quite a bit	Extreme-ly
1. Do physically demanding tasks?	1	2	3	4	5
2. Grip things tightly (e.g. turning on faucets)?	1	2	3	4	5
3. Carry things?	1	2	3	4	5

In the past two weeks , how much have you been bothered by ...	Not at all	A little	Mod-erately	Quite a bit	Extreme-ly
4. Problems with your balance?	1	2	3	4	5
5. Difficulties moving around indoors?	1	2	3	4	5
6. Being clumsy?	1	2	3	4	5
7. Stiffness?	1	2	3	4	5
8. Feelings of heaviness in your arms or legs?	1	2	3	4	5
9. Tremors in your arms or legs?	1	2	3	4	5
10. Spasms in your arms or legs?	1	2	3	4	5
11. Your body not doing what you want it to do?	1	2	3	4	5
12. Having to depend on others to do things for you?	1	2	3	4	5

Please make sure that you have answered all the questions before going on to the next page.

1

© 2000 Neurological Outcome Measures Unit, [name]

f:\institut.cultadap\project\pf1940\question\us_english\msisusaq.doc-23/05/2003

CONFIDENTIAL

The information contained herein may not be used, disclosed, or published without the written consent of Biogen Idec MA Inc.

In the past two weeks, how much have you been bothered by ...	Not at all	A little	Moderately	Quite a bit	Extremely
13. Limitations in your social and leisure activities at home?	1	2	3	4	5
14. Being stuck at home more than you would like to be?	1	2	3	4	5
15. Difficulties using your hands in everyday tasks?	1	2	3	4	5
16. Having to cut down on the amount of time you spent on work or other daily activities?	1	2	3	4	5
17. Problems using transportation (e.g. car, bus, train, taxi, etc.)?	1	2	3	4	5
18. Taking longer to do things?	1	2	3	4	5
19. Difficulty doing things spontaneously (e.g. going out on the spur of the moment)?	1	2	3	4	5
20. Needing to go to the bathroom urgently?	1	2	3	4	5
21. Feeling unwell?	1	2	3	4	5
22. Problems sleeping?	1	2	3	4	5
23. Feeling mentally fatigued?	1	2	3	4	5
24. Worries related to your MS?	1	2	3	4	5
25. Feeling anxious or tense?	1	2	3	4	5
26. Feeling irritable, impatient, or short tempered?	1	2	3	4	5
27. Problems concentrating?	1	2	3	4	5
28. Lack of confidence?	1	2	3	4	5
29. Feeling depressed?	1	2	3	4	5

Please make sure that you have circled ONE number for EACH question.

2

© 2000 Neurological Outcome Measures Unit, [name]

f:\institut.cultadap\project\p1940\questionius.english\msisusaq.doc-23/05/2003

[Hobart 2001]

CONFIDENTIAL

The information contained herein may not be used, disclosed, or published without the written consent of Biogen Idec MA Inc.
